10.2 THE RESPIMAT INHALER

Instructions for Use

[figure not shown]
RESPIMAT inhaler

How to use your RESPIMAT[®] inhaler

This leaflet explains how to use and care for your RESPIMAT[®] inhaler. ***Please read and carefully follow these instructions.***

The RESPIMAT[®] inhaler releases medication slowly and gently, making it easy to inhale it into your lungs.

The RESPIMAT[®] inhaler enables you to inhale the medicine contained in a cartridge. ***You will need to use this inhaler only ONCE A DAY. Each time you use it take 2 PUFFS.*** In the box you will find the RESPIMAT[®] inhaler and the RESPIMAT[®] cartridge. Before the RESPIMAT[®] inhaler is used for the first time, the cartridge provided must be inserted.

RESPIMAT[®] inhaler and the RESPIMAT[®] cartridge

Inserting the cartridge and preparation for use

The following steps 1-6 are necessary before first use:

 
1
	
1 With the grey cap closed, press the safety catch (E) and pull off the clear base (G).

 
2a
	
2 Take the cartridge (H) out of the box. Push the narrow end of the cartridge into the inhaler until it clicks into place (2a). The cartridge should be pushed gently against a firm surface to ensure that it has gone all the way in (2b).
 
Do not remove the cartridge once it has been inserted into the inhaler.

 
2b
	
 
3
	
3
 
Replace the clear base (G).
 
Do not remove the clear base again.

[figure not shown]
To prepare the RESPIMAT[®] inhaler for first-time use

 
4
	
4 Hold RESPIMAT[®] inhaler upright, with the grey cap (A) closed. Turn the clear base (G) in the direction of the red arrows on the label until it clicks (half a turn).

 
5
	
5 Open the grey cap (A) until it snaps fully open.

 
6
	
6 Point the RESPIMAT[®] inhaler towards the ground. Press the dose release button (D). Close the grey cap (A).
 
Repeat steps 4, 5 and 6 until a cloud is visible.
 
Then repeat steps 4, 5 and 6 three more times to ensure the inhaler is prepared for use.
 
Your RESPIMAT[®] inhaler is now ready to use.
 
These steps will not affect the number of doses available. After preparation your RESPIMAT[®] inhaler will be able to deliver 60 puffs.

Using the RESPIMAT[®] inhaler

You will need to use this inhaler only ONCE A DAY.

Each time you use it take 2 PUFFS.

 
I
	
I Hold RESPIMAT[®] inhaler upright, with the grey cap (A) closed, to avoid accidental release of dose. Turn the clear base (G) in the direction of the red arrows on the label until it clicks (half a turn).

 
II
	
II Open the grey cap (A) until it snaps fully open. Breathe out slowly and fully, and then close your lips around the end of the mouthpiece without covering the air vents (C). Point your RESPIMAT[®] inhaler to the back of your throat. While taking in a slow, deep breath through your mouth, press the dose release button (D) and continue to breathe in slowly for as long as you can. Hold your breath for 10 seconds or for as long as comfortable.
 
III Repeat steps I and II so that you get the full dose.
 
You will need to use this inhaler only ONCE A DAY.
 
Close the grey cap until you use your RESPIMAT[®] inhaler again.
 
If the RESPIMAT[®] inhaler has not been used for more than 3 days release one puff towards the ground. If the RESPIMAT[®] inhaler has not been used for more than 21 days repeat steps 4 to 6 until a cloud is visible. Then repeat steps 4 to 6 three more times.

When to get a new RESPIMAT[®] inhaler

 
Empty
 
Respimat[®] Inhaler
 
Boehringer Ingelheim Pharma GmbH [name]
 
CC 0123
 
361c/ENG/1
 
Full
 
turn
	
The RESPIMAT[®] inhaler contains 60 puffs (30 doses). The dose indicator shows approximately how many doses are left. When the pointer enters the red area of the scale, there is, approximately, medication for 14 puffs (7 days) left.
 
Once the dose indicator has reached the end of the red scale (i.e., all 30 doses have been used), the RESPIMAT[®] inhaler is empty and locks automatically. At this point, the base cannot be turned any further.

--	--

What if...

What if...	Reason	What to do
I can't turn the base easily.	
a) The RESPIMAT[®] inhaler is already prepared and ready to use.
 
b) The RESPIMAT[®] inhaler is locked after 60 puffs (30 doses).
	
a) The RESPIMAT[®] inhaler can be used as it is.
 
b) Prepare and use your new RESPIMAT[®] inhaler.

I can't press the dose release button.	The clear base has not been turned.	Turn the clear base until it clicks . (half a turn)
The clear base springs back after I have turned it.	The clear base was not turned far enough.	Prepare the RESPIMAT [®] inhaler for use by turning the clear base until it clicks . (half a turn)
I can turn the clear base past the point where it clicks.	Either the dose release button has been pressed, or the clear base has been turned too far.	With the grey cap closed, turn the base until it clicks . (half a turn)

How to care for your inhaler

Clean the mouthpiece including the metal part inside the mouthpiece with a damp cloth or tissue only, at least once a week.

Any minor discoloration in the mouthpiece does not affect the performance of your RESPIMAT[®] inhaler.

If necessary, wipe the outside of your RESPIMAT inhaler with a damp cloth.

Further information

The RESPIMAT[®] inhaler must not be disassembled after inserting the cartridge and replacing the clear base.

Do not touch the piercing element inside the base.

Keep out of the reach and sight of children.

Do not freeze.

Boehringer Ingelheim Pharma GmbH & Co. KG

[name]

0123 HI-Master-Version-04-BI 1744 + tiotropium combination-Respimat-20090831

10.3 RETURN OF INHALERS/CARTRIDGES

Return of Malfunctioning RESPIMAT inhalers

RESPIMAT inhalers, with the used cartridge in situ, that appeared to malfunction, will be returned to Boehringer Ingelheim Int'l Trading (Shanghai) Co., Ltd by responsible CRA as soon as possible.

The following information should be included in malfunction report form when the inhaler is returned:

- a) Medication number
- b) Visit number
- c) Date of malfunction
- d) Description of malfunction and cause of malfunction (if known)
- e) Person identifying malfunction
- f) Trial number

Investigator's name/center number

The original version of the Returned Inhaler Form should be included with the returned inhaler. A copy should be filed in Section 4 of ISF.

All inhalers and cartridges should be wrapped in bubble wrap or a similar packing material, placed in a secure shipping box (not a packing envelope) and shipped. Any questions regarding shipping and handling should be directed to the CML.

10.4 ADDITIONAL INFORMATION REGARDING IN/ EX CRITERIA

FEV₁ and FVC - Pulmonary Function Testing

The qualifying pulmonary function tests (FEV₁ and FVC) will be conducted at the screening visit (Visit 1) for reviewing eligibility of the patient.

Spirometers and their use, including daily calibration, must meet ATS/ERS criteria [[P05-12782](#)]. Spirometry will be conducted with the patient in a seated position and it is preferable that the same trained individual performs the PFTs for a given patient. At each time point, spirometric maneuvers will be conducted in triplicate. The highest FEV₁ and FVC from an acceptable maneuver will be recorded regardless of whether they come from different spirometric maneuvers or from the same maneuver. The 24-hour clock time of the **first** maneuver for each PFT time point will be recorded.

Reversibility testing [[P05-12782](#)]

At the screening visit (Visit 1), following the completion of 3 acceptable pre-bronchodilator forced expiratory manoeuvres, salbutamol will be administered to each patient in order to document the degree of reversibility. Immediately after (within 10 min) pre-bronchodilator forced expiratory manoeuvres and after a gentle and incomplete expiration, a dose of 100 µg of salbutamol is inhaled in 1 breath to total lung capacity (TLC). The breath is then held for 5-10 s before the subject exhales. Four separate doses (total dose 400 µg) are delivered at approximately 30-s intervals (this dose ensures that the response is high on the salbutamol dose-response curve). Three additional, acceptable post-bronchodilator forced expiratory manoeuvre tests are recorded ≥10 min and up to 15 min later after the last dose of salbutamol is inhaled.

Calculation of predicted normal values according to ECSC [[R94-1408](#)]

For height measured in inches

Males: FEV_1 predicted (L) = 4.30 x [height (inches)/39.37] - 0.029 x [age (yrs)] - 2.49

Females: FEV_1 predicted (L) = 3.95 x [height (inches)/39.37] - 0.025 x [age (yrs)] - 2.60

For height measured in meters

Males: FEV_1 predicted (L) = 4.30 x [height (m)] - 0.029 x [age (yrs)] - 2.49

[figure not shown]
Females: FEV_1 predicted (L) = 3.95 x [height (m)] - 0.025 x [age (yrs)] - 2.60

Ethnic adjustments may be made as appropriate as per ATS/ERS recommendations (R94-1408).

Calculation of number of pack years

Pack years = $\frac{\text{Number of cigarettes/day}}{20}$ x years of smoking

11. DESCRIPTION OF GLOBAL AMENDMENT

Number of global amendment		1
Date of CTP revision		13 Jul 2016
EudraCT number		NA
BI Trial number		1237.30
BI Investigational Products		Tiotropium+olodaterol RESPIMAT solution for inhalation. Olodaterol RESPIMAT solution for inhalation
Title of protocol		An open-label trial to assess pharmacokinetics and safety of tiotropium + olodaterol fixed-dose combination (5 µg/ 5 µg) and olodaterol 5µg delivered by the RESPIMAT inhaler after single and multiple dose treatment in Chinese patients with Chronic Obstructive Pulmonary Disease (COPD)
To be implemented only after approval of the IRB / IEC / Competent Authorities		
To be implemented immediately in order to eliminate hazard – IRB / IEC / Competent Authority to be notified of change with request for approval		
Can be implemented without IRB / IEC / Competent Authority approval as changes involve logistical or administrative aspects only		
Section to be changed		Synopsis
Description of change		 Was changed to : 
Rationale for change		Site was changed

Section to be changed		Synopsis and section 3.3.1 Main diagnosis for trial entry
Description of change		‘approximately sex ratio: 1:1’ was changed to ‘at least 1/3 of each gender’
Rationale for change		To meet the lowest criteria of CFDA

Section to be changed		4.1.2 Method of assigning patients to treatment groups
Description of change		‘Note that the medication number is same with the patient number (the latter is assigned at trial entry)’ was changed to ‘Note that the medication number is different from the patient number (the latter is assigned at trial entry)’
Rationale for change		As in patients trial eCRF will collect screening failure patients data, this process can’t guarantee the patient number and medication number are same

Section to be changed		5.4.2 Methods of sample collection The 4th paragraph
Description of change		‘After completion of each blood drawing procedure, the indwelling catheter can be filled with up to 0.5 mL of sterile heparinised saline (50 IU heparin/mL 0.9% saline) in order to prevent clotting.’ ’ was changed to ‘After completion of each blood drawing procedure, the indwelling catheter maybe filled with up to 0.5 mL of sterile heparinised saline (50 IU heparin/mL 0.9% saline) if necessary to prevent clotting.’
Rationale for change		To maintain flexible for action of prevent clotting.

Number of global amendment		2
Date of CTP revision		20 Feb 2017
EudraCT number		NA
BI Trial number		1237.30
BI Investigational Products		Tiotropium+olodaterol RESPIMAT solution for inhalation. Olodaterol RESPIMAT solution for inhalation
Title of protocol		An open-label trial to assess pharmacokinetics and safety of tiotropium + olodaterol fixed-dose combination (5 µg/ 5 µg) and olodaterol 5µg delivered by the RESPIMAT inhaler after single and multiple dose treatment in Chinese patients with Chronic Obstructive Pulmonary Disease (COPD)
To be implemented only after approval of the IRB / IEC / Competent Authorities		
To be implemented immediately in order to eliminate hazard – IRB / IEC / Competent Authority to be notified of change with request for approval		
Can be implemented without IRB / IEC / Competent Authority approval as changes involve logistical or administrative aspects only		
Section to be changed		Synopsis and section 3.3.1 Main diagnosis for trial entry
Description of change		‘at least 1/3 of each gender’ was deleted
Rationale for change		According to experience of Japanese Phase II trial and PI , It is almost impossible to recruit 1/3 female patient

Section to be changed		Synopsis,section 1-7
Description of change		‘and olodaterol 5µg ’ was deleted
Rationale for change		Olodaterol 5µg treatment group is unnecessary for NDA application.

Section to be changed		Section 6.2.2.1
Description of change		'15 min prior to the training administration of placebo' was changed to '5min (\pm 5 min) before the trial drug administration'
Rationale for change		To Keep consistent with Flow Chart and section 5.4.2

Section to be changed		Synopsis, section 3.3.1 and 7.7
Description of change		'32 (at least 24 completed)' was changed to '16 (at least 12 completed)' 'trial could be ended in case 12 evaluable patients are available'
Rationale for change		Olodaterol 5 μ g treatment group is unnecessary for NDA application.

Section to be changed		Flow Chart, Section 3.1 and 4
Description of change		'The first 16 recruited patients will be assigned to the olodaterol treatment and the other patients will be assigned to tiotropium + olodaterol FDC treatment' was deleted
Rationale for change		Olodaterol 5 μ g treatment group is unnecessary for NDA application.

Section to be changed		Section 7.4
Description of change		'To support new drug submission for olodaterol in China and to fulfil the timeline requirement by CFDA, the database will be locked after the last patient in olodaterol treatment group completes/withdraws from the trial. Interim analyses will be performed including all the planned analyses on pharmacokinetic and safety endpoints for patients treated by olodaterol. This will be the basis of the primary clinical trial report

		
and submission to regulatory agencies. A final database lock will be done once the last patient treated with tiotropium+olodaterol FDC completes the extended follow-up visit. The final clinical trial report will include analysis results of all patients in both treatment groups.’
 
Was changed to
 
‘No interim analyses is planned.’

Rationale for change		
Olodaterol 5µg treatment group is unnecessary for NDA application.

APPROVAL / SIGNATURE PAGE
Document Number: c07779972
Technical Version Number:3.0
Document Name: clinical-trial-protocol-version-03

Title: An open-label trial to assess pharmacokinetics and safety of tiotropium + olodaterol fixed-dose combination (5 µg/ 5 µg) delivered by the RESPIMAT inhaler after single and multiple dose treatment in Chinese patients with Chronic Obstructive Pulmonary Disease (COPD)

Signatures (obtained electronically)

Meaning of Signature	Signed by	Date Signed
Approval-Clinical Pharmacokinetics		20 Feb 2017 09:40 CET
Approval-Team Member Medicine		20 Feb 2017 20:41 CET
Approval-Clinical Monitor		21 Feb 2017 03:17 CET
Approval-Team Member Medicine		21 Feb 2017 05:56 CET
Approval-Biostatistics		21 Feb 2017 14:45 CET

(Continued) Signatures (obtained electronically)

Meaning of Signature	Signed by	Date Signed
-----------------------------	------------------	--------------------

[figure not shown]

## **2. LIST OF ABBREVIATIONS**

Term	Definition / description
ADS	Analysis data set
AE	Adverse event
BAC	Benzalkonium chloride
BI	Boehringer Ingelheim
bpm	beats per minute
COPD	Chronic Obstructive Pulmonary Disease
CTP	Clinical Trial Protocol
DBL	Database lock
ECG	Electrocardiogram
ECSC	European Community for Steel and Coal
EDTA	Ethylene diamine tetraacetic acid
EX	Exclusion criterion
FEV 1	Forced expiratory volume in one second
FVC	Forced vital capacity
GOLD	Global Initiative for Chronic Obstructive Lung Disease
HR	Heart rate
ICF	Informed consent form
ICH	International Conference on Harmonisation
MedDRA	Medical Dictionary for Regulatory Activities
MQRM	Medical Quality Review Meeting
ms	milliseconds
O*C	Oracle Clinical
PK	Pharmacokinetics
PR interval	The ECG interval from the start of the P wave to the start of the QRS complex
PT	Preferred term
PV	Protocol violation
QRS complex	Combination of Q wave, R wave, and S wave
QT interval	The ECG interval from the start of the QRS complex to the end of the T wave

---

Proprietary confidential information © 2017 Boehringer Ingelheim International GmbH or one or more of its affiliated companies

---

Term	Definition / description
QTc interval	QT interval, heart rate corrected
QTcF interval	QT interval, corrected according to Fridericias formula
RPM	Report planning meeting
RR interval	The ECG interval from the peak of the R wave to the peak of the subsequent R wave
SD	Standard deviation
SGOT	Serum glutamic oxaloacetic transaminase
SGPT	Serum glutamic pyruvic transaminase
SOC	System organ class
TSAP	Trial statistical analysis plan

### **3. INTRODUCTION**

As per International Conference on Harmonisation (ICH) E9, the purpose of this document is to provide a more technical and detailed elaboration of the principal features of the analysis described in the protocol, and to include detailed procedures for executing the statistical analysis of the primary and secondary variables and other data.

This trial statistical analysis plan (TSAP) assumes familiarity with the Clinical Trial Protocol (CTP), including Protocol Amendments. In particular, the TSAP is based on the planned analysis specification as written in CTP Section 7 “Statistical Methods and Determination of Sample Size”. Therefore, TSAP readers may consult the CTP for more background information on the study, e.g., on study objectives, study design and population, treatments, definition of measurements and variables, planning of sample size, randomisation.

SAS® Version 9.4 will be used for all analyses.

#### **4. CHANGES IN THE PLANNED ANALYSIS OF THE STUDY**

There has been no change in the planned analyses from the statistical methods described in the CTP.

## 5. ENDPOINTS

### 5.1 PRIMARY ENDPOINTS

No efficacy endpoint is defined for this trial. The objective of this trial is to assess the pharmacokinetics (PK) and safety of tiotropium + olodaterol fixed dose combination (5 µg/5 µg). The primary endpoints are specified as defined in the CTP, Sections 5.1.1.

### 5.2 SECONDARY ENDPOINTS

The secondary endpoints are specified as defined in the CTP, Sections 5.1.2.

### 5.4 OTHER VARIABLES

#### Demographic data:

- Gender: Male, Female
- Age [years]
- Race
- Height [cm]
- Weight [kg]
- Body mass index [kg/m^2]
- Smoking status: Never smoked, Ex-smoker, Currently smokes
- Smoking history [pack years]

#### History of trial indication:

- Trial diagnosis duration [days]

#### Treatment compliance:

Compliance [%] = (number of actual administered days) / (date of last trial drug administration – date of first trial drug administration + 1) × 100

#### Treatment exposure:

Extent of exposure [days] = date of last trial drug administration – date of first trial drug administration + 1 day

#### Pharmacokinetic:

The derivation of standard pharmacokinetic parameters will be performed according to 001-MCS-36-472 [\(1\)](#).

## **6. GENERAL ANALYSIS DEFINITIONS**

### **6.1 TREATMENTS**

Analysing treatments will be used for safety analysis. Date from the first trial drug intake up to 21 days after the last trial drug intake will be considered as on-treatment.

### **6.2 IMPORTANT PROTOCOL VIOLATIONS**

[Table 6.2: 1](#) gives the important protocol violations (PVs) for this trial. Patients with important PVs relevant to the evaluation of PK will be excluded from PK analysis. If data shows other important PVs, this table will be supplemented accordingly at the Database lock (DBL) meeting at latest.

Table 6.2: 1 Important protocol violations

Category / Code	Description	Comment/Example	Excluded from
A	Entrance criteria not met		
A1	Respiratory conditions		
A1.1	Without diagnosis of COPD	IN 2 not met Detected manually	None
A1.2	Age<40	IN 3 not met Detected manually	None
A1.3	Never smoke or ex-smokers with a smoking history of less than 10 packs year	IN 4 not met Detected automatically	None
A1.4	Patients are not capable to enter the trial	IN 5 not met Detected manually	None
A1.5	Patients are unable to inhale medication	IN 6 not met Detected manually	None
A1.6	Women of childbearing potential but are unable to use effective methods in birth control	IN 7 not met or EX 23 met Detected manually	None
A2	Exclusion criteria met		
A2.1	With significant disease other than COPD	EX1 Detected manually	None
A2.2	With clinically relevant abnormal baseline haematology, blood chemistry, or urinalysis	EX2 Detected manually Detected automatically for SGOT, SGPT, bilirubin, creatinine	None
A2.3	With asthma	EX3 Detected manually	None
A2.4	Patients are under conditions specified in exclusion criteria 4-14	EX4-14 Detected manually	None
A2.5	Have undergone thoracotomy with pulmonary resection	EX15 Detected manually	None
A2.6	Treated with any oral $\beta$ -adrenergics	EX16 Detected manually	None
A2.7	Treated with oral corticosteroid medication at unstable dose	EX17 Detected manually	None
A2.8	Regularly use daytime oxygen therapy	EX18 Detected manually	None
A2.9	Completed a pulmonary rehabilitation program in the six weeks prior to visit 1 or currently in the program	EX19 Detected manually	None
A2.10	Insufficient wash-out period	EX20 Detected manually	None

Category / Code	Description	Comment/Example	Excluded from
A2.11	Hypersensitivity to $\beta$ -adrenergics and/or anticholinergic drugs, BAC, EDTA or any other component of the RESPIMAT inhalation solution	EX21 Detected manually	None
A2.12	Pregnant or nursing women	EX22 Detected manually	None
A2.13	Patients who were in this study or are currently participating another study	EX24 Detected manually	None
A2.14	Patients who are unable to comply with pulmonary medication restrictions prior to allocation	EX25 Detected manually	None
B	Informed consent		
B1	Informed consent not available/not done	Informed consent date missing. No signature on ICF  Detected automatically/manually	All
B2	Informed consent too late	Date of informed consent was after the date of any study-related procedure. If date of informed consent equals to date of Visit 1, such cases will be discussed at MQRM/RPM/DBL meetings.  Detected automatically/manually	None
C	Trial medication and randomisation		
C1	Study medication taken >2 weeks longer than planned	Study medication was documented to be taken for >5 weeks  Detected automatically	case by case discussion before DBL if fraudulent data detected
C2	Serious non-compliance as reported in monitoring report	Detected manually	None
D	Concomitant Medication		
D1	Prohibited medication use during study	Review concomitant therapies  Detected manually.	None
E	Incorrect timing		
E1	Incorrect timing – visit	Only for PK endpoints Detected manually	PK set
E2	Incorrect timing – examination	Only for PK endpoints Detected manually	PK set

**KEY:** EX = exclusion criterion, SGOT = serum glutamic oxaloacetic transaminase, SGPT = serum glutamic pyruvic transaminase, BAC = benzalkonium chloride, EDTA = ethylene diamine tetraacetic acid, ICF = informed consent form, MORM = medical quality review meeting, RPM = report planning meeting

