5.4.2 Methods of sample collection

Blood sampling

Date and exact clock time of administration as well as of pharmacokinetic blood sampling have to be recorded. A blank blood sample will be collected prior to drug administration (i.e. at Visit 2, 5min (\pm 5 min) before the trial drug administration). Blood samples shall be drawn as close to the planned time as possible.

The time point zero for pharmacokinetic sampling is defined as end of (last) inhalation. Exact time points of plasma sampling will be documented in the eCRFs by the medical personnel. These actual sampling times will be used for the determination of pharmacokinetic parameters.

For quantification of drug plasma concentrations, about 6 mL of blood will be taken from a forearm vein using a blood collection tube containing potassium EDTA as anticoagulant blood drawing tube at the times indicated in the [Flow chart](#).

After completion of each blood drawing procedure, the indwelling catheter can be filled with up to 0.5 mL of sterile heparinised saline (50 IU heparin/mL 0.9% saline) in order to prevent clotting (per local clinical practice). Prior to every new blood drawing a small blood volume (approximately 0.5 mL) must be aspirated and discarded in order to avoid contamination of blood samples with heparin.

The EDTA-anticoagulated blood samples will be centrifuged as soon as possible after collection (within 40 min). Centrifugation will last for about 10 min (at about 2000 x g to 4000 x g) at room temperature or below. Two aliquots of at least 1 mL EDTA plasma samples will be obtained. One aliquot is intended for analysis of olodaterol, the second aliquot for analysis of tiotropium. Plasma samples will be frozen within 90 min after sampling and stored at the study site at about -20°C or below.

Detailed instructions for shipment of plasma samples are provided in the ISF or lab manual. In order to avoid contamination of plasma samples, study personnel are required to wash their hands with soap prior to collecting the plasma or handling of plasma samples. The RESPIMAT inhalers should be handled with gloves on and these gloves should be changed and discarded as soon as any container for PK samples is touched. As soon as the plasma is

obtained from the blood, gloves should again be changed. Plasma vials should be stored closed and only opened if necessary for the procedure.

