7.5 HANDLING OF MISSING DATA

7.5.1 Plasma concentration - time profiles

Concentration data identified with NOS (no sample), NOR (no valid result), NOA (not analysed), BLQ (below the limit of quantification) will be ignored and not replaced by zero at any time point (applies also to the lag phase including the pre-dose value). Descriptive statistics of concentrations at specific time points will be calculated only when at least 2/3 of the individuals have concentrations within the validated concentration range. The overall sample size to decide whether the “2/3 rule” is fulfilled will be based on the total number of samples intended to be drawn for that time point (i.e. BLQ, NOR, NOS, NOA are included). Every effort will be made to include all concentration data in an analysis. If not possible a case by case decision is required whether the value should only be excluded from half-life estimation or the complete analysis.

- If a concentration is only excluded from half life determination, it will be used for all other calculations (e.g. descriptive statistics) and for graphical presentation.

- If a concentration value is excluded from all calculations, it will not be presented graphically or used for the calculation of descriptive statistics and parameter determination. However, the excluded concentration itself will be listed in the tables in the CTR associated with an appropriate flag.

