10. APPENDICES

10.1 PHARMACOKINETIC METHODS

Concentrations will be used for calculations in the format that is reported in the bioanalytical report. The data format for descriptive statistics of concentrations will be identical with the data format of the respective concentrations. For the calculation of PK parameters, only concentrations within the validated concentration range will be used. The descriptive statistics of PK parameters will be calculated using the individual values with the number of decimal places as provided by the evaluation program. Then the individual values as well as the descriptive statistics will be reported with three significant digits in the CTR. The actual sampling times will be used. For pre-dose samples, the actual sampling time will be set to zero. Noncompartmental PK parameters will be determined using WinNonlin or another validated program.

Analyte plasma concentrations will be plotted graphically versus time for all subjects as listed in the analyte plasma concentration-time tables. For the presentation of the mean profiles, the arithmetic mean and the planned blood sampling times will be used.

Individual $C_{\max(ss)}$ and $t_{\max(ss)}$ values will be directly determined from the plasma concentration time profiles of each subject. If the same $C_{\max(ss)}$ concentration occurs at different time points, $t_{\max(ss)}$ is assigned to the first occurrence of $C_{\max(ss)}$.

AUC: The area under the curve will be calculated using the linear up/log down algorithm. If an analyte concentration is equal to or higher than the preceding concentration, the linear trapezoidal method will be used. If the analyte concentration is smaller than the preceding concentration, the logarithmic method will be used.

Linear trapezoidal rule ($t_2 > t_1$ and $C_{t_2} \geq C_{t_1}$):

The area of the trapezoid between the two data points (t_1, C_{t_1}) and (t_2, C_{t_2}) will be computed by:

$$AUC_{t_1-t_2} = 0.5 \times (t_2 - t_1) \times (C_{t_1} + C_{t_2})$$

Logarithmic trapezoid rule ($t_2 > t_1$ and $C_{t_2} < C_{t_1}$):

The area of the trapezoid between the two data points (t_1, C_{t_1}) and (t_2, C_{t_2}) will be computed by:

$$AUC_{t_1-t_2} = \frac{(t_2 - t_1) \times (C_{t_2} - C_{t_1})}{\ln(C_{t_2}/C_{t_1})}$$

$MRT_{ih,ss}$: $MRT_{ih,ss}$ calculation in the steady state will be performed according to the

following equation:

$$MRT_{ih,ss} = \frac{AUMC_{ss}}{AUC_{r,ss}}$$

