### **6.3 PATIENT SETS ANALYSED**

- **Treated set:**  
This patient set includes all patients who were dispensed study medication and were documented to have taken at least one dose of investigational treatment.
- **PK set:**  
This patient set includes all patients in the treated set with at least one evaluable PK parameter in the treatment period. The patients with important PVs related to PK will be excluded from PK set.

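### SAP rows E1/E2 remove the whole patient from the PK set for a timing violation, discarding primary PK values that the violation cannot have affected

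*SAP*

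**What the plan says.** **SAP.** Table 6.2:1 lists incorrect visit timing (E1) and incorrect examination timing (E2). Both rows carry the comment "Only for PK endpoints Detected manually", and the exclusion column names the PK set. Section 6.2 states: "Patients with important PVs relevant to the evaluation of PK will be excluded from PK analysis". Section 6.3 repeats it: "The patients with important PVs related to PK will be excluded from PK set". Entry to the same set is generous; it takes "all patients in the treated set with at least one evaluable PK parameter in the treatment period". Elsewhere in the table, row C1 allows case-by-case discussion, and serious non-compliance (C2) and prohibited medication (D1) lead to no exclusion. Section 4 declares: "There has been no change in the planned analyses from the statistical methods described in the CTP".

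**Protocol.** Section 5.4.2 has sampling times recorded and says: "These actual sampling times will be used for the determination of pharmacokinetic parameters". Appendix 10.1 agrees ("The actual sampling times will be used"), except that a pre-dose sample is given time zero. Under section 7.5.2 a missing actual time is generally replaced by the planned one. Section 7.5.1 sets the principle: "Every effort will be made to include all concentration data in an analysis". Where that is not possible, the decision concerns the single concentration: drop it from the half-life estimate only, or from everything.

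**The concern.** The comment in E1/E2 limits which timing errors count. It does not limit the consequence to the visit or value concerned. Once a violation is judged important and PK-relevant, the written result is loss of the patient from every PK table, for both analytes and both profiles.

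The Day 1 profile is complete before anything at Visit 3 or Visit 4 happens, so a later timing error cannot change it. The SAP nevertheless discards it for a completer, while the one-parameter entry rule keeps the same Day 1 values for a patient who stops after Visit 2. The more complete patient can thus contribute less. In a trial of 12 to 16 patients whose primary output is the description of these parameters, that is avoidable loss of valid primary data, and it follows from a manual judgement made after the data exist.

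**Working it through.** **The plan's own figure.** Protocol 7.7 wants 12 patients and assumes 25% dropout: 12 / (1 - 0.25) = 16. This reproduces and is not in dispute.

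**Primary values per patient (protocol 5.1.1).** Per analyte:

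- Single dose: Cmax, tmax, AUC0-6 = 3
- Multiple dose: Cmax,ss, tmax,ss, AUC0-6,ss, AUCτ,ss, Cpre,ss = 5
- Accumulation ratios, each using both visits = 2

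That is 3 + 5 + 2 = 10 parameters, and 10 x 2 analytes = 20 values.

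**What each violation can reach.** Protocol 5.4.1 derives the parameters at Visit 2 and Visit 4. The Visit 3 samples (5 days x 2 = 10) serve the steady-state assessment.

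| Timing violation | Primary values it can affect | Values it cannot affect | Values removed under E1/E2 |
|---|---|---|---|
| Visit 4 timing, or a mistimed dose between Day 1 and Visit 4 | at most (5 + 2) x 2 = 14 | 3 x 2 = 6 | 20 |
| Mistimed Visit 2 sample | at most (3 + 2) x 2 = 10 | 5 x 2 = 10 | 20 |
| Mistimed Visit 3 sample only | 0 | 20 | 20 |

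The last column applies only if the violation is judged important and PK-relevant. For comparison, a patient who stops after Visit 2 and has an evaluable Day 1 profile keeps 6 values.

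The needless loss is therefore 6/20 = 30% of the patient's primary values for a Visit 4 violation, 10/20 = 50% for a Visit 2 sample, and 20/20 = 100% for a Visit 3 sample.

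**Where actual times help and where they do not.** For a post-dose sample, the actual time places the concentration correctly on the curve for AUC and tmax, although a late sample can still miss the peak. Three cases are not cured:

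- A mistimed pre-dose sample at Visit 4, because its time is set to zero. It bears on Cpre,ss, on the two steady-state AUCs and on the AUC accumulation ratio.
- An altered dosing history, which protocol 4.1.4 recognises may influence data at Visits 3 and 4.
- Summaries at planned times, and the steady-state model that compares trough and 20-minute concentrations between days (protocol 7.3.5).

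In each case the affected values can be named, and none of them is a Day 1 parameter.

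**Weight of one patient.** 1/12 = 8.3%; 1/16 = 6.3%. The plan states no variability, so the following is only an illustration with an assumed geometric CV. The 95% interval for a geometric mean is the estimate multiplied and divided by exp(t x s / √n), with t on n - 1 degrees of freedom and s = √ln(1 + CV²).

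| Assumed CV | n = 12 | n = 11 |
|---|---|---|
| 30% | 1.205 | 1.218 |
| 50% | 1.350 | 1.373 |

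Losing one patient costs little precision. The issue is that valid values are lost for no analytical gain, and that the loss rests on a judgement.

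**Frequency.** The documents give no rate of timing errors and no criterion for when one is important. A probability of exclusion would need an assumed error rate per sample and would have to treat every error as important, so none is offered.

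**The case against.** The strongest reply is that the two documents address different things. Protocol 7.5.1 and 7.5.2 deal with missing data and individual concentrations; the protocol defines no PK set and no rule for patients with important violations. SAP section 3 describes the SAP as a more detailed elaboration. Value-level handling of ordinary deviations can coexist with patient-level removal for serious ones. This stands. A reader might infer that the SAP contradicts the protocol and that its section 4 statement is false; the texts do not prove that.

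Second, the trigger is filtered. A violation must be important, PK-relevant and found on manual review. A reader might infer that any late sample removes a patient. The text does not say so, and the Visit 3 sample case in particular may never be judged PK-relevant. Visit windows exist in the flow chart, and detailed windows may lie in timing charts or internal standards that are not shown. SAP 6.6 and 7.9 send PK data handling to such standards, which might also soften the consequence. Nothing shown does so, and 6.2 and 6.3 are explicit.

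Third, a reader might infer that an excluded patient still counts towards the 12 evaluable patients, so that a trial ended at 12 would be left with 11 and no replacement. Protocol 3.3.1 ties evaluability to available samples at Visits 2, 3 and 4 as laid out in the flow chart. Whether a badly mistimed sample meets that definition depends on the timing details not shown, so the inference is not established. Twelve is also a convention, with no hypothesis test behind it.

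Fourth, the protocol already reduces the risk: missed doses shortly before day 18 or Visit 4 lead to rescheduling (6.1, 6.2.2.3), and patients stay in the clinic from day 18. This lowers the likely frequency but leaves the written consequence unchanged.

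**Conclusion.** The point holds as a matter of proportion and consistency. Once a timing violation is judged important and PK-relevant, the SAP removes all 20 primary values of that patient. A Visit 4 violation can affect at most 14 of them; the 6 Day 1 values are lost although the violation cannot have touched them, and an early dropout would keep the same 6. This is broader than the protocol's value-level approach and is not declared in SAP section 4. It is best described as an undeclared narrowing of the analysed data.

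The conclusion rests on the patient-level wording of SAP 6.2 and 6.3, on parameters being derived only at Visits 2 and 4, and on no unseen standard overriding those sections. The number of patients affected is unknown and may be zero. The absence of a stated tolerance is not the issue; the patient-level consequence is. The change is worth making before database lock because it protects primary data at almost no cost, but the trial's conclusions do not depend on it.

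**What to change.** 1. In rows E1 and E2, replace the PK set entry with: *affected concentrations or parameters only*. State that this covers (a) Visit 4 parameters and the accumulation ratios when the dosing history is altered, and (b) the pre-dose concentration, Cpre,ss and any AUC or AUC ratio that depends on it when a pre-dose sample is mistimed, because its time is set to zero.
2. Align SAP 6.2 and 6.3 with this rule. For timing violations, remove a patient from the PK set only when no evaluable parameter remains.
3. Keep the non-compartmental analysis on actual times for post-dose samples.
4. Omit grossly mistimed samples from planned-time summaries and from the steady-state model, using a window stated or cited before database lock.
5. If removal of the whole patient is intended, declare it in SAP section 4 with the reason.

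The cost is SAP wording; no additional data are needed. The downside is that N will differ between parameter tables, which the one-parameter entry rule already allows. Each table should show its N and flag the excluded values.
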